For any subject who has not experienced progressive disease (PD) at the time of permanent discontinuation of venetoclax, follow-up phone calls will continue until death, discontinuation from the study or upon study completion.

Response criteria definitions are outlined in 2008 Modified IWCLL-WG Criteria for Tumor Response. See [Table 5](#).

For patients with only Partial Remission at Week 48 an additional CT and a bone marrow examination can be done between Week 48 and Week 108 to confirm CR if there is a possibility that a patient is in Complete Remission based on laboratory tests and a disease assessment physical examination.

NOTE: Disease assessments may be performed approximately 7 days prior to the scheduled visit.

Computed Tomography Scans (or Magnetic Resonance Imaging)

A CT scan with contrast will be accepted if previously performed within 35 days prior to the first dose of venetoclax. Otherwise, a CT scan must be performed within the Screening window (28 days) for all subjects. A CT scan will be performed for all subjects at Week 48 to confirm disease response. Contrast-enhanced CT scans including neck, chest, abdomen, and pelvis will be performed to assess response to treatment. A contrast-enhanced MRI of the neck, chest, abdomen and pelvis with a non-contrast CT scan of the chest may be used for subjects in whom a contrast CT is medically contraindicated (i.e., subjects with a severe allergy to CT contrast agents or subjects with impaired renal clearance). Whichever method is used at Screening should be consistently used throughout the duration of the study.

Any CT scan (or MRI) performed as standard of care throughout the study should be captured on the eCRF.

NOTE: CT scans (or MRI) may be performed 7 days prior to the scheduled visit.

Bone Marrow Aspirate and Biopsy

At baseline, a bone marrow aspirate and biopsy are not required; however results should be recorded if available. If the subject achieves a CR by clinical criteria and confirmatory CT scan, a bone marrow aspirate and biopsy will be performed to confirm the CR. Whenever possible the bone marrow aspirate for biomarker MRD assessment should be split from this sample. If a CT scan is performed and does not confirm a CR, a bone marrow biopsy should not be obtained.

Bone marrow aspirates and biopsies performed as standard of care throughout the study should also be captured on an eCRF.

Subject Calendars/Diaries

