- Absence of lymphadenopathy (nodes > 15 mm in longest diameter or any extra nodal disease) by physical examination and CT scan
- No hepatomegaly or splenomegaly by physical examination (as determined by measurement below the relevant costal margin)
- Absence of disease or constitutional symptoms (B symptoms: unexplained fevers > 38°C or 100.4°F, drenching night sweats, > 10% body mass weight loss in the preceding 6 months)
- Blood counts above the following laboratory values:
 - Neutrophils > $1.5 \times 10^9/L$ [1500/ μL] (without the need for exogenous growth factors)
 - Platelets > $100 \times 10^9/L$ [100,000/ μL] (without the need for platelet transfusion or exogenous growth factors)
 - Hemoglobin > 110 g/L [11 g/dL] (without the need for blood transfusions or exogenous erythropoietin)
- Bone marrow at least normocellular for age, < 30% of nucleated cells being lymphocytes. Lymphoid nodules should be absent. Bone marrow aspirate and biopsy should be performed after CR/CRi has been achieved. If the bone marrow is hypocellular, a repeat determination should be made in 4 weeks or when peripheral blood counts have recovered. A marrow biopsy should be compared to a pre-treatment marrow if available. Subjects who are otherwise

in a complete remission, but bone marrow nodules can be identified histologically should be considered to be nodular PR (nPR). Immunohistochemistry (IHC) should be performed to define whether these nodules are composed of primarily T cells or lymphocytes other than CLL cells, or CLL cells.

Complete Remission with Incomplete Marrow Recovery (CRi)

Subjects who fulfill the criteria for CR (including bone marrow) but who have persistent cytopenia (anemia or thrombocytopenia or neutropenia) apparently unrelated to CLL but related to drug toxicity will be considered CRi. The marrow evaluation described above should be performed with scrutiny and not show any clonal infiltrate.

Partial Remission (PR)

To be considered a PR at least 2 of the following must be met:

- $\geq 50\%$ decrease in peripheral blood lymphocyte count from the pretreatment baseline value.
- $\geq 50\%$ reduction in lymphadenopathy.
- $\geq 50\%$ reduction in the size of the liver and/or spleen (if abnormal prior to therapy).

In addition at least **one** of the following criteria must be met:

- Neutrophils $> 1,500/\mu\text{L}$ or $\geq 50\%$ improvement over baseline.
- Platelets $> 100,000/\mu\text{L}$ or $\geq 50\%$ improvement over baseline.

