- Hemoglobin $> 11.0 \text{ g/dL}$ or $\geq 50\%$ improvement over baseline without transfusions or exogenous growth factors.

Table 5. 2008 Modified IWCLL NCI-WG Criteria for Tumor Response

Parameter	Complete Remission (CR) All Criteria Must be Met^a	Partial Remission (PR) at Least 2 Criteria from Group A AND at Least 1 Criterion from Group B Must be Met	Progressive Disease (PD) at Least 1 Criterion from Group A OR 1 Criterion from Group B Must be Met^b	Stable Disease (SD) All Criteria Must be Met
Group A				
Lymphadenopathy	None > 1.5 cm	Decrease \geq 50% ^c	Increase \geq 50% ^d or any new LN > 1.5 cm	Change of -49% to +49% ^e
Blood Lymphocytes	< 4000/ μ L	Decrease \geq 50% from baseline	Increase \geq 50% over baseline (\geq 5000/ μ L)	Change of -49% to +49%
Hepatomegaly ^f	None	Decrease \geq 50%	Increase \geq 50% ^g	Change of -49% to +49%
Splenomegaly ^f	None	Decrease \geq 50%	Increase \geq 50% ^g	Change of -49% to +49%
Marrow	Normocellular, < 30% lymphocytes, no B lymphoid nodules; hypocellular marrow defines CRi	N/A	N/A	N/A
Group B				
Platelet Count	> 100,000/ μ L ^h	> 100,000/ μ L or increase \geq 50% over baseline ^h	Decrease of \geq 50% from baseline secondary to CLL	Change of -49% to +49%
Hemoglobin	> 11.0 g/dL ^h	> 11.0 g/dL or increase \geq 50% over baseline ^h	Decrease of > 2 g/dL from baseline secondary to CLL	Increase to \leq 11.0 g/dL over baseline, or decrease < 2 g/dL
Neutrophils	> 1500/ μ L ^h	> 1500/ μ L or increase \geq 50% over baseline ^h	Decrease \geq 50% from baseline secondary to CLL	N/A
New Lesions	None	None	Appearance of new palpable lymph nodes (> 1.5 cm in longest diameter) or any new extra nodal lesion (regardless of size) or transformation to a more aggressive histology, e.g., Richter Syndrome ^d	None

Table 5. 2008 Modified IWCLL NCI-WG Criteria for Tumor Response (Continued)

Parameter	Complete Remission (CR) All Criteria Must be Met ^a	Partial Remission (PR) at Least 2 Criteria from Group A AND at Least 1 Criterion from Group B Must be Met	Progressive Disease (PD) at Least 1 Criterion from Group A OR 1 Criterion from Group B Must be Met ^b	Stable Disease (SD) All Criteria Must be Met
Other Considerations				
Non-Target Lesions	Nodes must be normal size as visually estimated; extra nodal and other assessable disease should be absent	No change/decreased	Unequivocal progression	No change or decrease or non-substantial increase

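### The partial remission text counts liver and spleen as one criterion and Table 5 counts them as two, so one response pattern is PR under one current rule and not under the other

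*Protocol*

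**What the plan says.** Protocol Section 5.3.3.1, under Partial Remission, gives a list: "To be considered a PR at least 2 of the following must be met". The three items are lymphocytes, lymphadenopathy and a "reduction in the size of the liver and/or spleen (if abnormal prior to therapy"), each with a 50% threshold. One of three blood-count criteria is needed as well.

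Table 5 in the same section heads its PR column "Partial Remission (PR) at Least 2 Criteria from Group A AND at Least 1 Criterion from Group B Must be Met". Its Group A has separate rows for lymphadenopathy, lymphocytes, hepatomegaly and splenomegaly, each with a PR entry of a decrease of at least 50%; marrow does not apply to PR. Footnote f limits the organ rows to organs enlarged before therapy and does not merge them.

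Section 5.3.1.1, under Disease Assessments, says "Response criteria definitions are outlined in 2008 Modified IWCLL-WG Criteria for Tumor Response" and refers the reader to Table 5.

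SAP Section 10.1.1 takes PR by the named criteria as assessed by the investigator. It does not restate the items.

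**The concern.** Both definitions are current protocol text in the same section. An investigator working from the list and one working from the table can classify the same examination differently. Response is assessed by investigators at about 67 sites, and the documents describe no central review that would impose one reading.

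PR enters three planned summaries:

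- **ORR**, a secondary endpoint reported for the ITT, BCRi-naive and BCRi-experienced populations (SAP Section 10.2.2).
- **DOR**, which under SAP Section 10.1.1 includes only responders and starts at the earliest PR when PR comes before a deeper response.
- **MRD response by overall response category** (SAP Section 10.4).

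**Working it through.** The plan states no figure on this point, so there is none to reproduce. The check compares the two counting rules.

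**Inputs.** Text rule and Table 5 from Protocol Section 5.3.3.1; planned sizes of 250, 190 and up to 60 from Protocol Section 8.2; confirmation interval and best-response rule from SAP Section 10.1.1.

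**Set-up.** Let L, N, H and S equal 1 if lymphocytes, nodes, liver and spleen respectively fell by at least 50%, and 0 otherwise. Assume both organs were enlarged at baseline, a blood-count criterion is met under both rules, and the table's other PR entries are satisfied.

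- Text: PR if L + N + max(H, S) ≥ 2
- Table 5: PR if L + N + H + S ≥ 2

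| L + N | Patterns | PR by text | PR by Table 5 |
|---|---|---|---|
| 2 | 4 | 4 | 4 |
| 1 | 8 | 6 | 6 |
| 0 | 4 | 0 | 1 |
| All | 16 | 10 | 11 |

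The rules differ in one pattern: H = S = 1 with L = N = 0. For example, take liver −60%, spleen −60%, lymphocytes −20% and nodes −40%. The text count is 0 + 0 + 1 = 1 (not PR) and the table count is 0 + 0 + 1 + 1 = 2 (PR). The 16 patterns are not equally likely, so 1 in 16 is not a frequency.

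If the text's and/or is read as requiring both enlarged organs to shrink, max(H, S) becomes min(H, S). The text then gives 4 + 2 + 0 = 6 PRs, and the rules differ in 11 − 6 = 5 patterns, including the one above.

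The example subject does not fit stable disease either. Table 5 requires all its SD criteria, including organ changes between −49% and +49%. A site using the text for PR therefore has no category that fits.

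**Differences in the other direction.** Footnote h bars growth-factor and transfusion support for platelets, hemoglobin and neutrophils; the PR text attaches that condition to hemoglobin only. Take a subject with two disease items met whose only blood-count criterion is a neutrophil count above 1,500/µL on G-CSF, which Protocol Table 2 permits. That subject is PR by the text and not by the table. Table 5 also has PR entries for new lesions, non-target lesions and target extranodal disease that the text lacks.

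**Size.** A subject whose ORR status flips moves ORR by:

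- ITT: 1/250 = 0.40 points
- BCRi-naive: 1/190 = 0.53 points
- BCRi-experienced: 1/60 = 1.67 points

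The documents do not say how many subjects would flip. Assuming 1 to 5 of 250, the shift is 1/250 to 5/250, or 0.4 to 2.0 points. For scale, assume 188 of 250 responders (75.2%, close to the lower ORR of 75.0% quoted in Protocol Section 3.0). The exact 95% interval is 69.4% to 80.4%, a half-width of (80.4 − 69.4)/2 = 5.5 points.

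**The case against.** **The documents lean towards Table 5.** Section 5.3.1.1 sends the reader there, and the SAP uses the criteria name that titles the table. That is some support for treating the table as the reference. It is a cross-reference, though, not a statement that the table overrides the list. If the table is meant to govern, the list in Section 5.3.3.1 is wrong and still needs correcting.

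**The pattern is narrow and may seldom reach ORR.** This stands. Both organs must be enlarged and both must halve while lymphocytes and nodes do not. ORR uses the best response at any time, with assessments at Weeks 24, 36 and 48, and PR must be confirmed at not less than 49 days. A subject discordant at one visit may qualify at another, so that only the DOR start date changes, or nothing does. Eligibility does not exclude the pattern, since organomegaly alone can satisfy the measurable-disease criterion (Section 5.2.1).

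**The and/or wording is not itself a conflict.** On its natural reading, one responding organ earns one credit in both places. This also stands. What happens when one of two enlarged organs responds is an ambiguity to settle in the same edit.

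A reader might infer that the table can only add PRs, so that using the text would simply lower ORR. The documents do not support that: footnote h and the lesion entries can remove PRs that the text allows.

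**Conclusion.** The two PR rules conflict as written. With the blood-count and other table conditions met, shrinkage of both enlarged organs by at least 50%, without a 50% fall in lymphocytes or nodes, is PR by Table 5 and not by the text. The net direction across all the differences is not fixed.

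The effect on ORR is up to 0.4 points per subject in 250 and 1.7 per subject in 60, and applies only to subjects with no other qualifying response whose PR is confirmed. The affected share cannot be derived from the documents and is probably small. Under the assumed 1 to 5 subjects, the shift stays well inside the sampling uncertainty of ORR.

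A reader might also infer a threat to the main result. There is none: the primary endpoint counts only CR and CRi, both definitions of CR require no enlarged liver or spleen, and the power basis does not involve PR. ORR and DOR are secondary and no efficacy endpoint is formally tested (SAP Section 10.1). OS is unaffected. The point is a classification inconsistency in secondary and exploratory summaries.

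**What to change.** Reconcile the PR list in Section 5.3.3.1 and Table 5 to a single rule. It should state:

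- whether liver and spleen count as one criterion or two;
- how one responding organ counts when both were enlarged;
- which blood counts carry the no-growth-factor and no-transfusion condition;
- whether the new-lesion, non-target and extranodal entries are conditions for PR.

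The sponsor should choose the rule that matches the intended criteria; either organ count removes the discordant pattern. SAP Section 10.1.1 should then name that rule as the basis for investigator-assessed PR in ORR and DOR.

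The cost is a text or table edit, a note to sites and a sentence in the SAP. No new procedure is needed, because liver and spleen are already evaluated at each disease assessment. The sponsor should confirm that the eCRF holds a size for each organ: Section 5.3.3.1 asks for the presence of enlargement and is not clear that size is captured. If it is, a listing of subjects with both organs reduced by at least 50% would show the actual effect.

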following sites should be measured: cervical, supraclavicular, axillary, inguinal, and femoral. The presence of hepatomegaly and splenomegaly should be performed.

The 12 largest bi-dimensional lesions should be recorded in the eCRF.

- Target Lesions: A maximum of 12 target lesions may be selected (up to 6 nodal and 6 extra nodal). Target nodal lesions must be abnormal (> 1.5 cm in LDi [Longest Diameter] at baseline), clearly measurable and suitable for consistent, reproducible measurement in at least two perpendicular dimensions. Target extra nodal lesions must be > 1 cm in two perpendicular diameters at baseline.
- Non-Target Lesions: Sites will be classified as non-target lesions where disease is present but not selected for target lesions. A maximum of 10 non-target lesions can be selected. Non-target nodal lesions must be abnormal (> 1.5 cm in LDi at baseline). Non-target extra nodal lesions must be > 1 cm in two perpendicular diameters. Nodal and extra nodal lesions that were not selected as target lesions at baseline can be followed as non-target lesions.

Computed tomography (CT) is the preferred method to measure lesions selected for response assessment. CT scans (with contrast) should include neck, chest, abdomen, and pelvis scans. CT scans for response assessment may be limited to areas of prior involvement only, if required by local regulatory authorities. A contrast-enhanced MRI of the neck, chest, abdomen and pelvis with a non-contrast CT scan of the chest may be used if CT with contrast is medically contraindicated (e.g., severe contrast allergy). If MRIs are used instead of CT scans, MRIs should be used consistently throughout the study. Conventional CT and MRI should be performed with cuts of 5 mm or less in slice thickness contiguously. Spiral CT should be performed by use of 5 mm contiguous reconstruction algorithm; this specification applies to the regions of the neck, chest, abdomen and pelvis at baseline and follow-ups. The 12 largest bi-dimensional lesions should be recorded in the eCRF (6 nodal and 6 extra nodal).

For accurate overall response evaluation, ultrasound (US) should not be used to measure tumor lesions.

Details on bone marrow biopsy and aspirate are provided in Section 5.3.1.1. Study Procedures.

Tumor Response Criteria

Complete Remission (CR)

CR requires all of the following criteria:

- Peripheral blood lymphocytes (evaluated by blood and differential count) below $4 \times 10^9/L$ (4000/ μL)

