Target Extra Nodal Disease	Absence of any extra nodal disease by physical examination (palpable, visualized extra nodal) and CT scan	≥ 50% decrease in SPD	≥ 50% increase in the longest diameter of any extra nodal lesion	Not CR, CRi, PR, or PD

CLL = chronic lymphocytic leukemia; LN = lymph nodes; N/A = Not applicable; SPD = sum of the products of diameters; CRi = complete remission with incomplete marrow recovery

- a. CR also requires the lack of disease-related constitutional symptoms.
- b. Transformation to a more aggressive histology (e.g., Richter Syndrome) would also qualify as a PD.
- c. Sum of the products of multiple LNs (as evaluated by CT scans). Note in eCRF if by physical examination only.
- d. Increase in SPD of multiple nodes, or in greatest diameter of any previous site, or appearance of any new lymphadenopathy or organomegaly. Degree of change in LN or lymphocyte counts should be measured from nadir (lowest post-treatment) values.
- e. Sum products of up to 6 LNs or LN masses (target lesions), with no increase in an LN or new enlarged LN. Increase of < 25% in small LNs (< 2 cm) not significant. Decreases should be measured compared to baseline (pre-treatment) values.
- f. If enlarged before therapy.
- g. An increase in the previously noted enlargement of the liver or spleen by 50% or more or the de novo appearance of hepatomegaly or splenomegaly.
- h. Without the need for exogenous growth factors or transfusions.

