5.3.3.2 Definition of Disease Progression

Disease progression according to 2008 Modified IWCLL NCI-WG Criteria for Tumor Response is characterized by at least one of the following:

- Appearance of any new lesion, such as enlarged lymph nodes (> 1.5 cm), splenomegaly, hepatomegaly, or other organ infiltrates. An increase by 50% or more in greatest determined diameter of any previous site.
- An increase in the previously noted enlargement of the liver or spleen by 50% or more or the de novo appearance of hepatomegaly or splenomegaly.
- An increase in the number of blood lymphocytes by 50% or more with at least 5,000 B lymphocytes per microliter. The increase should be assessed against the best response while on study.
- Transformation to a more aggressive histology (e.g., Richter's Syndrome). Whenever possible, this diagnosis should be confirmed by lymph node biopsy. For subjects experiencing disease progression due to Richter's Syndrome while on study, supplemental data may be collected.
- Occurrence of cytopenia (neutropenia, anemia or thrombocytopenia) attributable to CLL.

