8.2 Demographic and Baseline Characteristics

Categorical baseline variables will be summarized with the number and percentage of subjects in each category. Continuous baseline variables will be summarized with descriptive statistics (number of non-missing observations, mean, standard deviation, median, maximum and minimum).

Categorical baseline variables include:

- Sex (male, female)
- Race (White, Black or African American, Asian, and Other)
- Geographic region (US, EUROPE)
- Ethnicity (Not Hispanic or Latino, and Hispanic or Latino)
- Age (< 65, ≥ 65, < 75, and ≥ 75)
- Tobacco use (current, former, never, and unknown)
- Alcohol use (current, former, never, and unknown)
- ECOG performance status (grade: 0, 1, 2)
- LDH (≤ ULN, > ULN)
- Prior number of oncology therapies (1, 2, ≥ 3)
- Previous line of Ibrutinib failure (1, > 1)
- Previous line of Idelalisib failure (1, > 1)
- 17p deletion status (deleted, not deleted, indeterminate)
- Rai stage (0, 1, 2, 3, 4)
- Binet stage (A, B, C)

- IgVH status (mutated, unmutated)
- ZAP-70 (positive, negative, indeterminate)
- CD-38 (positive, negative, indeterminate)
- Beta 2-microglobulin (< 3 mg/L, ≥ 3 mg/L)
- TP53 mutation (yes, no, unknown)
- 11q (deleted, not deleted, indeterminate)
- 13q (deleted, not deleted, indeterminate)
- 12q trisomy (present, not present, indeterminate)
- Absolute lymphocyte count (ALC) (< 25 × 10⁹/L, ≥ 25 × 10⁹/L; < 100 × 10⁹/L, ≥ 100 × 10⁹/L)
- Bulky disease nodes (< 5 cm, 5 cm To 10 cm, ≥ 10 cm)
- Prior BCRi treated (yes, no)
- TLS risk category-US (low, medium, high)
- TLS risk category-ROW (yes, no)
- Hospitalized for TLS prophylaxis before venetoclax (yes, no)

Continuous baseline variables include:

- Age (year)
- Weight (kg) by male and female
- Height (cm)
- Number of prior oncology therapy
- Beta-2 microglobulin (MG/L)
- Lactate dehydrogenase (LDH)
- Absolute lymphocytes count (10⁹/L)
- Bulky disease nodes (cm)
- Duration of BCRI therapy before venetoclax (month)

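### The protocol gives conflicting references for lymphocyte progression (baseline in the Table 5 cell, nadir in footnote d, best response in 5.3.3.2), and the SAP does not choose one for PFS, TTP and DOR

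*Protocol*

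**What the plan says.** The protocol states the lymphocyte criterion for progression in three places.

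- **Table 5 (Section 5.3.3.1), progressive-disease cell for blood lymphocytes:** "Increase \geq 50% over baseline (\geq 5000" (per µL). The reference is the pre-treatment value and the floor is in lymphocytes. In the text available, the cell carries no footnote marker; marker d stands on the lymphadenopathy and new-lesion cells.
- **Table 5, footnote d:** "Degree of change in LN or lymphocyte counts should be measured from nadir (lowest post-treatment) values".
- **Section 5.3.3.2:** "An increase in the number of blood lymphocytes by 50% or more with at least 5,000 B lymphocytes per microliter", followed by "The increase should be assessed against the best response while on study".

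Section 5.3.3.2 also says that progression "is characterized by at least one of the following", so the lymphocyte rule can define the event by itself. Section 5.3.1.1 (Disease Assessments) points investigators to Table 5 for the response definitions. SAP Section 10.1.1 runs TTP to the earliest progression, and PFS and DOR to the earliest progression or death. It does not say which lymphocyte reference applies. SAP Section 10.1 states that responses are those of the investigator.

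**The concern.** The same blood count can end a response under one line and continue it under another. Take a subject with a baseline count of 100, a nadir of 1 and a current count of 40 (all × 10⁹/L). Against baseline the count is down 60%, which is not progression by the table cell and still meets the lymphocyte part of partial remission. Against nadir it is a 40-fold rise and above 5, which is progression.

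The criterion matters in this schedule. Appendix D plans CT after baseline only at Week 48, and disease assessments only at Weeks 24, 36 and 48, while hematology continues at visits up to Week 108. After Week 48, blood counts and physical examination are therefore the main scheduled signals of progression. If investigators read different lines, the dates behind PFS, TTP and DOR are not on one scale, and nothing in the SAP brings them back to one.

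**Working it through.** The plan gives no event count or power for PFS, TTP or DOR, so there is no figure to reproduce.

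**Inputs**
- Rise of 50% and floor of 5 × 10⁹/L (5000/µL): Table 5 and Section 5.3.3.2. Total lymphocytes are used for both floors, because Protocol Table 4 lists a lymphocyte count and no B-lymphocyte count.
- Baselines of 25 and 100 × 10⁹/L: the SAP's own cut-points in Section 8.2, "Absolute lymphocyte count (ALC) (< 25 × 10⁹/L, ≥ 25 × 10⁹/L; < 100 × 10⁹/L, ≥ 100 × 10⁹/L". Baselines of 3, 5 and 10 are added because Section 5.2.1 allows entry on nodes or organomegaly without lymphocytosis.
- Nadir: not in the documents. Complete remission needs "Peripheral blood lymphocytes (evaluated by blood and differential count) below" 4 × 10⁹/L, so values of 0.5 to 4 are used as illustration.
- Doubling time after nadir: not in the documents. Assumed to be 1, 3, 6 or 12 months.

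**Formulas**
- Nadir threshold = max(1.5 × nadir, 5). For any nadir up to 5 / 1.5 = 3.3 this equals 5.
- Cell threshold = max(1.5 × baseline, 5).
- Doublings = log2(cell threshold / nadir threshold).
- Delay = doublings × doubling time, assuming exponential regrowth and no other progression criterion met first.

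**Results for a nadir of 3.3 or lower (× 10⁹/L)**

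| Baseline | Nadir threshold | Cell threshold | Ratio | Doublings | Delay in months at doubling times of 1, 3, 6, 12 months |
|---|---|---|---|---|---|
| 3 | 5 | 5 | 1 | 0 | 0, 0, 0, 0 |
| 5 | 5 | 7.5 | 1.5 | 0.58 | 0.6, 1.8, 3.5, 7.0 |
| 10 | 5 | 15 | 3 | 1.58 | 1.6, 4.8, 9.5, 19.0 |
| 25 | 5 | 37.5 | 7.5 | 2.91 | 2.9, 8.7, 17.4, 34.9 |
| 100 | 5 | 150 | 30 | 4.91 | 4.9, 14.7, 29.4, 58.9 |

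**Variations**
- Nadir of 4: the nadir threshold is 6, and the gap is log2(37.5 / 6) = 2.64 doublings at baseline 25 and log2(150 / 6) = 4.64 at baseline 100.
- A shallower fall, from 100 to 50: the thresholds are 75 and 150, one doubling apart.
- Best response against nadir: a complete responder's count is below 4, so the Section 5.3.3.2 threshold lies between 5 and 1.5 × 4 = 6, close to the nadir threshold. For partial responders the two on-study references can differ more if the lowest count does not fall at the best-response assessment.

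**Recorded dates.** Visits are monthly from Week 8 and every 3 months from Week 48, so recorded delays round to that spacing. Week 108 is 108 × 7 / 30.4 ≈ 25 months. The longest delays in the table exceed the whole main treatment period, so some of those events would appear as censoring.

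**The case against.** Two of the three places agree in rejecting the pre-treatment value: footnote d names lymphocyte counts outright, and the section devoted to defining progression gives an on-study reference. On this view one stray cell remains, and nothing shows that investigators followed it. The illustrated delays need a high baseline, a deep nadir and progression by lymphocytes alone. Nodes, liver or spleen, cytopenia due to CLL, or transformation may come first, and a count of 150 × 10⁹/L with none of these would be an extreme case. The endpoints affected are secondary, and SAP Section 10.1 plans no efficacy testing.

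Most of this stands, and it limits the size and reach of the point. It does not remove the contradiction. The cell says baseline in plain words, so a marker lost in the PDF reading would not explain it. Table 5 is the place to which sites are directed for response definitions, and the SAP does not settle the matter.

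A reader might go further and infer that PFS, TTP and DOR are inflated in this trial. The documents do not support that: they do not show which line was applied, they contain no lymphocyte kinetics, and the gap is nil for some subjects. A reader might also infer that nadir must be the right reference. Progression bears on whether treatment continues (Sections 5.1 and 5.4.1), so that choice belongs to the sponsor and its clinical team.

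**Conclusion.** This is an internal contradiction in the current protocol, and the SAP leaves it open. Its possible effect is confined to subjects with a raised baseline count whose first sign of progression is lymphocytosis. In them, with a nadir of 3.3 × 10⁹/L or lower, the threshold differs 7.5-fold at baseline 25 and 30-fold at baseline 100. Those ratios need no assumption about growth rate. The delays in months rest entirely on the assumed doubling time and on no other criterion being met first. The gap is small at baseline 5 and absent at about 3.3 or lower. If the table cell was used, PFS, TTP and DOR may be overstated in such subjects relative to the on-study readings. The primary endpoint, CR + CRi as best response, does not use the progression rule directly. The floor, lymphocytes in one place and B lymphocytes in another, is a second and related mismatch. The point should be corrected, but it does not threaten the primary analysis.

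**What to change.** - Reconcile the Table 5 cell, footnote d and the placement of its marker, and Section 5.3.3.2 to one reference (baseline, nadir or best response) and one floor (lymphocytes or B lymphocytes). If best response is chosen, say which count represents it.
- State the chosen reference and floor in SAP Section 10.1.1 under DOR, TTP and PFS, and send sites a clarification.
- Add a sensitivity analysis that dates lymphocyte progression under each reading from the local laboratory counts already entered in the eCRF, and report PFS, TTP and DOR each way. A text correction alone would not change progression dates already recorded.

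Two limits should be stated with that analysis. The B-lymphocyte floor can only be approximated by the total count. Appendix D schedules no hematology in post-treatment follow-up, so a subject taken off treatment at an early progression call may have no later counts with which to apply the baseline reading.

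The cost is a text correction, a site clarification and some extra programming and analysis. No new data are needed.
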